4.3. Secondary Outcomes

- Change in VAS Leg from preoperative baseline to 12 months +/- 3 months
- Change in VAS Back from preoperative baseline to 12 months +/- 3 months
- Change in Oswestry Disability Index (ODI) from baseline to 12 months +/- 3 months
- Intra-operative and post-operative adverse events

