The signature of the investigator below constitutes approval of this protocol and provides the necessary assurances that this Outcomes Study will be conducted according to Good Clinical Practices and to all stipulations, clinically and administratively, as stated in the protocol, including all statements as to confidentiality.

It is agreed that the protocol contains all necessary information required to conduct the Outcomes Study as outlined in the protocol.

PRINCIPAL INVESTIGATOR:

Print Name

Signature

Date

Table of Contents

Sponsor Protocol Approval Page	2
Investigator Protocol Approval Page	3
Table of Contents	4
Study Summary	5
Introduction (1)	6
Background (1.1)	6
Device Description (1.2)	6
Purpose of the Study (2)	7
Study Design (3)	7
Study Hypothesis (3.1)	7
Study Description (3.2)	7
Primary Outcome (3.3)	7
Secondary Outcomes (3.4)	7
Study Population (3.5)	7
Sample Size Justification (3.6)	8
Proposed Study Site List and Justification (3.7)	8
Subject Eligibility Criteria (3.8)	9
Inclusion Criteria (3.9)	9
Exclusion Criteria (3.10)	10
Study Procedure (4)	10
Subject Chart Review (4.1)	10
Data Collection Procedure (4.2)	10
Data to be Collected (4.3)	11
Data Management Plan (4.4)	13
Monitoring Plan (4.5)	13
Adverse Events (5)	13
Subject Safety (5.1)	14
Mitigation of Risks (5.2)	14
Image and Data Analysis (6)	15
Radiographic Fusion Assessment (6.1)	15
Data Analysis (6.2)	15
Ethical and Regulatory Requirements (7)	16
Code of Conduct (7.1)	16
Subject Confidentiality (7.2)	16
Retention of Records by Investigator (7.3)	16
References (8)	16

Integrity Implants Study Summary

Study Title:	Transforaminal/Posterior Lumbar Interbody Fusion with the FlareHawk® Expandable Interbody Fusion Device: A Retrospective Chart Review Study
Study Design:	Retrospective study – chart review
Study Purpose:	To evaluate the clinical outcomes of patients undergoing transforaminal or posterior lumbar interbody fusion (TLIF or PLIF) procedures using a FlareHawk expandable interbody fusion cage
Study Population:	Patients who underwent 1 or 2 contiguous level TLIF or PLIF procedure with the FlareHawk expandable interbody fusion cage. A total of at least 100 patients from at least three sites will be enrolled based on inclusion/exclusion criteria.
Minimum Follow-up:	12 months +/- 3 months
Primary Outcome:	Proportion of subjects with radiographic arthrodesis at 12 months +/- 3 months

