3.6 Sample Size Justification

The primary outcome of this study, radiographic arthrodesis, is commonly observed in approximately 80-100% of study subjects for TLIF/PLIF surgeries [FlareHawk CER-00001 Rev C]. With 100 subjects included, if an 88% fusion rate is observed, the 95% confidence interval¹ for fusion success will be 80.2%-93.0%, placing the performance results within the anticipated range. Further, the inclusion of at least 100 subjects will enable the likely detection of adverse events that have a probability of occurrence of at least 1.6%, assuming a power of 80% [MedDev 2.7.1, rev 4]. This detection rate is adequate for this device and study based on the severity and frequency of anticipated adverse events associated with the FlareHawk device [FlareHawk CER-00001 Rev C]. The target sample size for inclusion will be 118 patients, assuming that up to 15% will not have data at the 12 months follow-up, yielding at least 100 patients with data.

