For any adverse events, the observed rate of each type of event will be summarized as a percentage with the 95% confidence interval and compared with rates observed in the literature describing the current state of the art with other PLIF and TLIF interbody cages.

7. Ethical and Regulatory Requirements:

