(Open to Close)Estimated Blood Loss: cc./ml.Length of Hospitalization: daysFluoroscopic Exposure Time: min.**TYPE OF PROCEDURE**Operative Procedure: Open Mini-open Minimally Invasive Operative Approach: PLIF TLIF Number of Levels: One Two Surgery Levels: L2-L3 L3-L4 L4-L5 L5-S1 **IMPLANT(S) USED****Implant #1**

Shell Catalog # _____

Shim Catalog # _____

Shell Lot # _____

Shim Lot # _____

Implant #2NA

Shell Catalog # _____

Shim Catalog # _____

Shell Lot # _____

Shim Lot # _____

Implant #3NA

Shell Catalog # _____

Shim Catalog # _____

Shell Lot # _____

Shim Lot # _____

Implant #4NA

Shell Catalog # _____

Shim Catalog # _____

Shell Lot # _____

Shim Lot # _____

GRAFT MATERIALGraft Materials Used: Allograft Autograft Mix of Allograft/Autograft

Clinical Site Number:

Subject Number:

Case Report Form
Integrity Implants FlareHawk® Study
Surgery – Visit 2

SUPPLEMENTAL FIXATION

Supplemental Fixation Used (check one): Unilateral Bilateral

Description of Construct: _____

ADVERSE EVENTS (AEs)

Did any intra-operative adverse events occur? Yes No

If "Yes", add adverse event to **Intra-Operative AE Log**.

DELAY OF SURGERY

Device Related Delay of Surgery: Yes No

If yes, how many minutes? min.

If yes, cause of delay? _____

INSTRUMENTATION

Were there any reported issues with instrument(s)? Yes No

If yes, please provide the catalog and lot number below as well as the description of the issue with the instrument(s):

Catalog # _____ Description of issue: _____

Lot # _____

Not Recorded

Clinical Site Number:

Subject Number:

Case Report Form
Integrity Implants FlareHawk® Study
Surgery – Visit 2

RADIOGRAPHS

Are intra-operative, post-implantation X-rays available on CD? Yes No

X-ray views taken (*check those that apply*): AP Lateral

If X-rays are available, has the CD been provided to the evaluators? Yes No

ADDITIONAL COMMENTS

Please add any other pertinent information regarding the surgical procedure, the device/instruments or any safety concerns:

Clinical Site Number:

Subject Number:

Case Report Form
Integrity Implants FlareHawk® Study
Follow-up – Visit 3

Page 1 of 3

VISIT 3 – 12 MONTHS (+/- 3MONTHS)

DATE OF VISIT: / /
MM DD YYYY

RADIOGRAPHS

Are 12-month X-rays available on CD? Yes No

X-ray views taken (check those that apply): AP Lateral Flexion/Extension

If X-rays are available, has the CD been provided to the evaluators? Yes No

ADVERSE EVENTS (AEs)

Did any post-operative adverse events occur? Yes No

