Dural tear/injury	Yes 	No 				
Nerve root injury	Yes 	No 				
Other Adverse Events (Describe event below)			Severity	Relatedness	Action Taken	Outcomes

Clinical Site Number:

Subject Number:

Case Report Form
Integrity Implants FlareHawk® Study
 Post-Operative Adverse Event Log

POST-OPERATIVE ADVERSE EVENT (AE) LOG **No AEs Recorded**

If Adverse Events have occurred, check “yes” or “no” for each event listed below. If “yes” is marked for an Adverse Event below, please complete all of the columns to the right.

Adverse Events	Yes / No		Onset Date	Resolution Date	Severity	Relatedness	Action Taken	Outcomes
			MM/DD/YYYY	MM/DD/YYYY	1- None 2- Mild 3- Moderate 4- Severe 5- Death	1- Device related 2- Procedure related 3- Not related	1- None 2- Medication/ Therapy 3- Revision Surgery 4- Additional Surgery 5- Other	1- Resolved 2- Ongoing at 12-month (+/- 3 month) Follow-up 3- Unknown
Infection	Yes 	No 	/ /	/ /				
Donor site pain	Yes 	No 	/ /	/ /				
Complex regional pain syndrome	Yes 	No 	/ /	/ /				
Urinary retention/difficulty	Yes 	No 	/ /	/ /				
Ipsilateral or contralateral radiculopathy	Yes 	No 	/ /	/ /				
Device component breakage/fracture	Yes 	No 	/ /	/ /				
Device or device component migration/retropulsion	Yes 	No 	/ /	/ /				
Device complication (e.g. loss of expansion)	Yes 	No 	/ /	/ /				
Device subsidence	Yes 	No 	/ /	/ /				
Loss of fixation	Yes 	No 	/ /	/ /				
Non-union	Yes 	No 	/ /	/ /				
Vertebral fracture	Yes 	No 	/ /	/ /				
Adjacent segment disease	Yes 	No 	/ /	/ /				

Clinical Site Number:

Subject Number:

Case Report Form
Integrity Implants FlareHawk® Study
 Post-Operative Adverse Event Log

POST-OPERATIVE ADVERSE EVENT (AE) LOG Continued

No AEs Recorded

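### Post-operative adverse-event rates are crude percentages with no stated window or denominator, so late events are not measured over a common duration before comparison with the literature

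*Combined protocol and SAP*

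**What the plan says.** Attachment A section 6.2, repeated in section 9.2 of protocol CP-00001, provides that "the observed rate of each type of event will be summarized as a percentage with the 95% confidence interval" and that these rates are "compared with rates observed in the literature describing the current state of the art with other PLIF and TLIF interbody cages". Neither section names a time point, a denominator, a time-to-event method or any matching on length of follow-up.

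The outcome lists (CP-00001 sections 4.2 and 4.3; Attachment A sections 3.3 and 3.4) tie fusion, VAS and ODI to 12 ± 3 months. The safety outcome is given only as "Intra-operative and post-operative adverse events". The Study Summary labels 12 ± 3 months "Minimum Follow-up" and gives no maximum.

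On numbers, Attachment A section 3.6 aims to include 118 and gives the reason: "assuming that up to 15% will not have data at the 12 months follow-up, yielding at least 100 patients with data". It also states that 100 subjects give 80% power to detect events with a probability of at least 1.6%, without saying over what period.

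On the case report form, intra-operative events are asked about on the surgery page. The question that opens the post-operative log, "Did any post-operative adverse events occur", stands on the Visit 3 page. The extra follow-up forms carry a visit date but cover only VAS and ODI. The post-operative log has onset and resolution dates, and one of its outcome codes is "Ongoing at 12-month (+/- 3 month) Follow-up". No form shown has a field for last chart contact.

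**The concern.** Several events on the post-operative log can take months to appear: subsidence, migration, loss of fixation and adjacent segment disease. For these, a percentage means little unless the period over which it accrued is known. Here the period differs between patients. For a patient without Visit 3 it cannot be established, because a log with no events does not separate a patient followed event-free for a year from one who left after a few weeks.

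Safety is part of the study's stated purpose, and the literature comparison is the only benchmark that section 6.2 gives for adverse events. If duration is not aligned, a difference from published rates, or the absence of one, may reflect follow-up and not the device. The bias can run either way: patients who leave early lower the percentage, and chart time beyond 12 months raises it.

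**Working it through.** **The plan's own figures.** All three reproduce, so the sample-size arithmetic is not at fault.
- Detection: 1 − (1 − 0.016)^100 = 80.07%. Solving for exactly 80% gives a probability of 1.597%, stated as 1.6%.
- Inclusion target: 100 / 0.85 = 117.6, rounded up to 118. Up to 118 − 100 = 18 patients may lack 12-month data.
- Wilson interval for 88/100: 80.2% to 93.0%.

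**Inputs for the follow-up check.** From the documents: Visit 3 at 9 to 15 months; 118 included; 100 with 12-month data. Assumed, because the documents give no event rate: a true 12-month risk R of 1.6%, 5% or 10%, and a constant hazard. The crude percentage when everyone is followed for t months is then 1 − (1 − R)^(t/12).

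| R at 12 months | t = 9 | t = 12 | t = 15 |
|---|---|---|---|
| 1.6% | 1.20% | 1.60% | 2.00% |
| 5% | 3.77% | 5.00% | 6.21% |
| 10% | 7.60% | 10.00% | 12.34% |

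For example, 1 − 0.95^(9/12) = 3.77% and 1 − 0.95^(15/12) = 6.21%. If events begin only after month 6 and reach 5% by month 12, the crude figure is 2.53% at 9 months and 7.41% at 15.

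These are the ends of the window. If visits are spread evenly around 12 months the two ends nearly cancel: (3.77 + 6.21) / 2 = 4.99%. The distortion appears when visits cluster towards one end.

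**Patients without 12-month data.** Take R = 5%, with 100 patients followed to 12 months and all 118 in the denominator.
- The 18 contribute no follow-up: 100 × 0.05 / 118 = 4.24%.
- The 18 are lost at 3 months: 4.43%.
- The 18 are lost at 6 months: 4.62%.
- Only the 100 in the denominator: 5.00%.

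The choice of denominator alone therefore moves the figure between 4.2% and 5.0%.

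**If chart entries after Visit 3 also count.** For the stated surgery dates (1 December 2017 to 31 May 2018), available chart time is 13.6 to 19.5 months at Attachment A's date of 18 July 2019, and 17.5 to 23.5 months at 15 November 2019. With R = 5%, the constant-hazard percentage is 7.41% at 18 months and 9.75% at 24.

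**Detection claim.** With R = 1.6% and n = 100, the chance of seeing at least one event is 70.2% at 9 months, 80.1% at 12 and 86.7% at 15. The stated 80% thus presupposes a duration that the plan does not give.

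**The case against.** The strongest reply is that ascertainment is better than the Visit 3 question suggests. Attachment A section 4.3 asks for post-operative device- or procedure-related events from the record of every included subject, as available. The log is a separate form with dates, blanks must be explained, and missing entries are queried. A reader might infer that patients without Visit 3 are never asked about; the documents do not support that. What stands is narrower: the form does not make explicit that the log is completed without Visit 3, and it does not record how long such patients were observed.

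A reader might also infer that event collection is open-ended. That rests on silence. The outcome code tied to the 12-month visit implies an end there, although it classifies how an event ended and does not limit when it began. Nor do the documents say that patients lost early stay in the denominator; the 1.6% calculation uses 100 subjects, which fits a denominator of those with data equally well.

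A much larger effect could be constructed. With an assumed 10% risk, one could take 0.10 × 0.85 = 8.5% at one end and 1 − 0.9^(23.5/12) = 18.6% at the other. This is not a credible range for the study. The low end needs all missing patients to contribute nothing, and the high end gives every patient the chart time of the earliest one, up to a document date that is not a data cut-off.

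Three further points are right. Crude percentages suit intra-operative events. Fusion, and so the main evidence on non-union, is already graded on 12 ± 3 month films. Sampling error is also large: the Wilson interval for 5/100 is 2.2% to 11.2%, wider than the 3.8% to 6.2% spread. But that interval does not cover a bias from follow-up, so it does not answer the point. Finally, the data processing and monitoring plans cited in sections 4.4 and 4.5 are not part of the document and might settle some of this.

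**Conclusion.** The concern holds for late post-operative events. The planned estimator has no stated window or denominator, follow-up differs by design, and time at risk is unknown for some patients. Nothing aligns duration with the literature before the comparison. Under an assumed constant hazard, a 5% 12-month risk could read about 3.8% to 6.2% across the Visit 3 window, and about 4.2% if 18 of 118 add nothing but are counted. The figure would be higher still if later chart entries are included. These are illustrations at the edges, not forecasts; the real shift depends on when visits fell and who is missing.

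It does not follow that the rates cannot be compared with the literature at all. Surgery, onset and Visit 3 dates are collected, so a fixed-time estimate is already possible for patients with Visit 3. The plan does not call for one, and without a last-contact date the remaining patients cannot be censored properly. The plan should be changed before the safety analysis is run, but the point does not undermine the study as a whole.

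**What to change.** 1. Make explicit that the post-operative log is completed for every included patient, whether or not Visit 3 exists, and add one field: date of last chart contact.
2. Keep crude percentages for intra-operative events, with the denominator stated.
3. For each post-operative event type, state the denominator of the crude percentage. Beside it, report cumulative incidence at 12 months after surgery with a 95% confidence interval, censoring at last contact and treating death as a competing event. List later events separately.
4. Compare with published rates of similar follow-up duration, and use crude against crude where the source reports crude rates.

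The cost is one date field, one instruction, a standard analysis and slightly more chart abstraction. One limitation remains: radiographic events carry the date they were detected, not their true onset. An event first seen on a film taken between 12 and 15 months would fall after the 12-month cut, which is why the separate list and the crude percentage should stay in the report.

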7.1 Code of Conduct

The Investigator will ensure that the clinical study is conducted in accordance with good clinical practice (GCP), EN ISO 41455, and all regulatory and institutional requirements, including those for subject privacy, informed consent, Independent Ethics Committee (IEC)/Institutional Review Board (IRB) approval and record retention, and the Food and Drug Administration (FDA) Guidelines for the conduct of clinical trials. As this study is a retrospective chart review adding no additional risk to the subjects, a waiver of informed consent will be requested from the IEC/IRB.

7.2 Subject Confidentiality

The Sponsor will maintain the confidentiality of the identity of all subjects enrolled in the study and the information contained in their records. The Sponsor will also instruct the study investigators in the importance of maintaining the confidentiality of study records. The subject records will be made available as required for review by governing regulatory agencies and a reviewing IEC/IRB, however to every extent possible; the subject’s identities will not be disclosed. Compliance with EN ISO 14155 and the Health Insurance Portability and Accountability Act of 1996 (HIPAA) is required and data collection must comply with the Standards for Privacy of Individually Identifiable Health Information, 45 CFR Part 160 and Part 164, as amended from time to time (the “Privacy Rule”), under HIPAA.

The case report forms do not include any subject identifying information in accordance with HIPAA. Therefore, once the data is entered on the CRF, a subject can no longer be identified. It is the responsibility of the investigator to maintain a list of subject identification and ID numbers.

2. Has the subject been diagnosed with degenerative disc disease of the lumbar spine based on clinical and radiological evidence?	 Yes	 No
3. Has the subject been treated with PLIF or TLIF surgery using the FlareHawk expandable cage(s) at 1 or 2 contiguous levels from L2-S1?	 Yes	 No
4. Has the subject undergone surgery using the FlareHawk expandable interbody fusion cage, according to approved labeling, prior to September 30, 2018?	 Yes	 No
All inclusion criteria must be answered "Yes" to proceed to completing the remaining fields. If any inclusion criteria were answered "No" do not collect additional data.		

EXCLUSION CRITERIA		
1. Does the subject have a history of fusion surgery at the study level(s) prior to treatment with the FlareHawk device(s)?	 Yes	 No
2. Did the subject have spondylolisthesis unable to be reduced to grade 1 as part of the surgical procedure?	 Yes	 No
3. Has the subject had surgery with the FlareHawk device(s) at more than 2 levels?	 Yes	 No
4. Has the subject had surgery with the FlareHawk device(s) at levels outside the range of L2- S1?	 Yes	 No
5. Has the subject been treated with any bone grafting material other than autogenous or allogenic bone graft in the FlareHawk device(s) and surrounding disc space?	 Yes	 No
6. Did the subject have any contraindications listed in the approved labeling?	 Yes	 No
All exclusion criteria must be answered "No" to proceed to completing the remaining fields. If any exclusion criteria were answered "Yes" do not collect additional data		

ELIGIBILITY		
Did the Subject meet the Eligibility Criteria?	 Yes	 No

Clinical Site Number: Subject Number:

Case Report Form
Integrity Implants FlareHawk® Study
Baseline Data – Visit 1

Page 1 of 3

VISIT 1 – BASELINEDATE OF VISIT: //
MM DD YYYY**DEMOGRAPHIC DATA**Date of Birth: //
MM DD YYYY Gender at Birth: Female
Male
Height: in. Weight: lb.**SMOKING STATUS**Non-smoker Active smoker History of smoking Not Recorded **COMORBID CONDITIONS**Hypertension Diabetes Obesity (BMI ≥ 30)
Hypercholesterolemia Coronary Heart Disease Hyperthyroidism
Active Cancer History of Cancer
If checked, type of cancer: _____ If checked, type of cancer: _____
None recorded **VISUAL ANALOG SCALE (VAS)**Please enter the VAS score as documented at the baseline visit in the medical records for the level of **RIGHT LEG** pain.VAS **Right Leg** Pain Score: _____ Not Recorded Please enter the VAS score as documented at the baseline visit in the medical records for the level of **LEFT LEG** pain.VAS **Left Leg** Pain Score: _____ Not Recorded Please enter the VAS score as documented at the baseline visit in the medical records for the level of **BACK** pain.VAS **Back Pain** Score: _____ Not Recorded

Clinical Site Number: Subject Number:

Case Report Form
Integrity Implants FlareHawk® Study
Baseline Data – Visit 1

OSWESTRY DISABILITY INDEX (ODI)

Please transcribe answers directly from the patient's medical record.
(Circle score for each section recorded)

Not Recorded

Section 1 – Pain Intensity	
0	I have no pain at the moment
1	The pain is very mild at the moment
2	The pain is moderate at the moment
3	The pain is fairly severe at the moment
4	The pain is very severe at the moment
5	The pain is the worst imaginable at the moment

Section 4 – Walking	
0	Pain does not prevent me walking any distance
1	Pain prevents me from walking more than 1 mile
2	Pain prevents me from walking more than ½ mile
3	Pain prevents me from walking more than 100 yards
4	I can only walk using a cane or crutches
5	I am in bed most of the time

Section 2 – Personal Care (washing, dressing, etc.)	
0	I have no pain at the moment
1	The pain is very mild at the moment
2	The pain is moderate at the moment
3	The pain is fairly severe at the moment
4	The pain is very severe at the moment
5	The pain is the worst imaginable at the moment

Section 5 – Sitting	
0	I can sit in any chair as long as I like
1	I can only sit in my favorite chair as long as I like
2	Pain prevents me from sitting more than one hour
3	Pain prevents me from sitting more than 30 minutes
4	Pain prevents me from sitting more than 10 minutes
5	Pain prevents me from sitting at all

Section 3 – Lifting	
0	I can lift heavy weights without extra pain
1	I can lift heavy weights but it gives extra pain
2	Pain prevents me from lifting heavy weights off the floor, but I manage if they are conveniently placed e.g. on a table
3	Pain prevents me lifting heavy weights, but I can manage light to medium weights if they are conveniently positioned
4	I can lift very light weights
5	I cannot lift or carry anything at all

Section 6 – Standing	
0	I can stand as long as I want without extra pain
1	I can stand as long as I want but it gives me extra pain
2	Pain prevents me from standing more than 1 hour
3	Pain prevents me from standing more than 30 minutes
4	Pain prevents me from standing for more than 10 minutes
5	Pain prevents me from standing at all

Clinical Site Number:

Subject Number:

Case Report Form
Integrity Implants FlareHawk® Study
 Baseline Data – Visit 1

OSWESTRY DISABILITY INDEX (ODI) Continued

Please transcribe answers directly from the patient's medical record.
 (Circle score for each section recorded)

Not Recorded

Section 7 – Sleeping	
0	My sleep is never disturbed by pain
1	My sleep is occasionally disturbed by pain
2	Because of pain I have less than 6 hours sleep
3	Because of pain I have less than 4 hours sleep
4	Because of pain I have less than 2 hours sleep
5	Pain prevents me from sleeping at all

Section 8 – Sex Life (if applicable)	
0	My sex life is normal and causes no extra pain
1	My sex life is normal but causes some extra pain
2	My sex life is nearly normal but is very painful
3	My sex life is severely restricted by pain
4	My sex life is nearly absent because of pain
5	Pain prevents any sex life at all

Section 9 – Social Life	
0	My social life is normal and gives me no extra pain
1	My social life is normal but increases the degree of pain
2	Pain has no significant effect on my social life apart from limiting my more energetic interests e.g. sports
3	Pain has restricted my social life and I do not go out as often
4	Pain has restricted my social life to my home
5	I have no social life because of pain

Section 10 – Traveling	
0	I can travel anywhere without pain
1	I can travel anywhere but it gives me extra pain
2	Pain is bad but I manage journeys over two hours
3	Pain restricts me to journeys of less than one hour
4	Pain restricts me to short necessary journeys under 30 minutes
5	Pain prevents me from traveling except to receive treatment

Clinical Site Number: Subject Number: **Case Report Form**
Integrity Implants FlareHawk® Study
Surgery – Visit 2

Page 1 of 3

VISIT 2 – SURGERYDATE OF SURGERY: / /
MM DD YYYYTotal Operative Time: min.
(Open to Close)Estimated Blood Loss: cc./ml.Length of Hospitalization: daysFluoroscopic Exposure Time: min.**TYPE OF PROCEDURE**Operative Procedure: Open Mini-open Minimally Invasive Operative Approach: PLIF TLIF Number of Levels: One Two Surgery Levels: L2-L3 L3-L4 L4-L5 L5-S1 **IMPLANT(S) USED****Implant #1**

Shell Catalog # _____

Shim Catalog # _____

Shell Lot # _____

Shim Lot # _____

Implant #2NA

Shell Catalog # _____

Shim Catalog # _____

Shell Lot # _____

Shim Lot # _____

Implant #3NA

Shell Catalog # _____

Shim Catalog # _____

Shell Lot # _____

Shim Lot # _____

Implant #4NA

Shell Catalog # _____

Shim Catalog # _____

Shell Lot # _____

Shim Lot # _____

GRAFT MATERIALGraft Materials Used: Allograft Autograft Mix of Allograft/Autograft

Clinical Site Number:

Subject Number:

Case Report Form
Integrity Implants FlareHawk® Study
Surgery – Visit 2

SUPPLEMENTAL FIXATION

Supplemental Fixation Used (check one): Unilateral Bilateral

Description of Construct: _____

ADVERSE EVENTS (AEs)

Did any intra-operative adverse events occur? Yes No

If "Yes", add adverse event to **Intra-Operative AE Log**.

DELAY OF SURGERY

Device Related Delay of Surgery: Yes No

If yes, how many minutes? min.

If yes, cause of delay? _____

INSTRUMENTATION

Were there any reported issues with instrument(s)? Yes No

If yes, please provide the catalog and lot number below as well as the description of the issue with the instrument(s):

Catalog # _____ Description of issue: _____

Lot # _____

Not Recorded

Clinical Site Number:

Subject Number:

Case Report Form
Integrity Implants FlareHawk® Study
Surgery – Visit 2

RADIOGRAPHS

Are intra-operative, post-implantation X-rays available on CD? Yes No

X-ray views taken (*check those that apply*): AP Lateral

If X-rays are available, has the CD been provided to the evaluators? Yes No

ADDITIONAL COMMENTS

Please add any other pertinent information regarding the surgical procedure, the device/instruments or any safety concerns:

Clinical Site Number:

Subject Number:

Case Report Form
Integrity Implants FlareHawk® Study
Follow-up – Visit 3

Page 1 of 3

VISIT 3 – 12 MONTHS (+/- 3MONTHS)

DATE OF VISIT: / /
MM DD YYYY

RADIOGRAPHS

Are 12-month X-rays available on CD? Yes No

X-ray views taken (check those that apply): AP Lateral Flexion/Extension

If X-rays are available, has the CD been provided to the evaluators? Yes No

ADVERSE EVENTS (AEs)

Did any post-operative adverse events occur? Yes No

If "Yes", add adverse event to **Post-Operative AE Log**.

VISUAL ANALOG SCALE (VAS)

Please enter the VAS score as documented at the follow-up visit in the medical records for the level of **RIGHT LEG** pain.

VAS **Right Leg** Pain Score: _____ Not Recorded

Please enter the VAS score as documented at the follow-up visit in the medical records for the level of **LEFT LEG** pain.

VAS **Left Leg** Pain Score: _____ Not Recorded

Please enter the VAS score as documented at the follow-up visit in the medical records for the level of **BACK** pain.

VAS **Back Pain** Score: _____ Not Recorded

Clinical Site Number:

Subject Number:

Case Report Form
Integrity Implants FlareHawk® Study
 Follow-up – Visit 3

OSWESTRY DISABILITY INDEX (ODI)

Please transcribe answers directly from the patient's medical record.
 (Circle score for each section recorded)

Not Recorded

Section 1 – Pain Intensity	
0	I have no pain at the moment
1	The pain is very mild at the moment
2	The pain is moderate at the moment
3	The pain is fairly severe at the moment
4	The pain is very severe at the moment
5	The pain is the worst imaginable at the moment

Section 4 – Walking	
0	Pain does not prevent me walking any distance
1	Pain prevents me from walking more than 1 mile
2	Pain prevents me from walking more than ½ mile
3	Pain prevents me from walking more than 100 yards
4	I can only walk using a cane or crutches
5	I am in bed most of the time

Section 2 – Personal Care (washing, dressing, etc.)	
0	I have no pain at the moment
1	The pain is very mild at the moment
2	The pain is moderate at the moment
3	The pain is fairly severe at the moment
4	The pain is very severe at the moment
5	The pain is the worst imaginable at the moment

Section 5 – Sitting	
0	I can sit in any chair as long as I like
1	I can only sit in my favorite chair as long as I like
2	Pain prevents me from sitting more than one hour
3	Pain prevents me from sitting more than 30 minutes
4	Pain prevents me from sitting more than 10 minutes
5	Pain prevents me from sitting at all

Section 3 – Lifting	
0	I can lift heavy weights without extra pain
1	I can lift heavy weights but it gives extra pain
2	Pain prevents me from lifting heavy weights off the floor, but I manage if they are conveniently placed e.g. on a table
3	Pain prevents me lifting heavy weights, but I can manage light to medium weights if they are conveniently positioned
4	I can lift very light weights
5	I cannot lift or carry anything at all

Section 6 – Standing	
0	I can stand as long as I want without extra pain
1	I can stand as long as I want but it gives me extra pain
2	Pain prevents me from standing more than 1 hour
3	Pain prevents me from standing more than 30 minutes
4	Pain prevents me from standing for more than 10 minutes
5	Pain prevents me from standing at all

Clinical Site Number: Subject Number:

Case Report Form
Integrity Implants FlareHawk® Study
Follow-up – Visit 3

Page 3 of 3

OSWESTRY DISABILITY INDEX (ODI) Continued

Please transcribe answers directly from the patient's medical record.

Not Recorded **Section 7 – Sleeping**

0	My sleep is never disturbed by pain
1	My sleep is occasionally disturbed by pain
2	Because of pain I have less than 6 hours sleep
3	Because of pain I have less than 4 hours sleep
4	Because of pain I have less than 2 hours sleep
5	Pain prevents me from sleeping at all

Section 8 – Sex Life (if applicable)

0	My sex life is normal and causes no extra pain
1	My sex life is normal but causes some extra pain
2	My sex life is nearly normal but is very painful
3	My sex life is severely restricted by pain
4	My sex life is nearly absent because of pain
5	Pain prevents any sex life at all

Section 9 – Social Life

0	My social life is normal and gives me no extra pain
1	My social life is normal but increases the degree of pain
2	Pain has no significant effect on my social life apart from limiting my more energetic interests e.g. sports
3	Pain has restricted my social life and I do not go out as often
4	Pain has restricted my social life to my home
5	I have no social life because of pain

Section 10 – Traveling

0	I can travel anywhere without pain
1	I can travel anywhere but it gives me extra pain
2	Pain is bad but I manage journeys over two hours
3	Pain restricts me to journeys of less than one hour
4	Pain restricts me to short necessary journeys under 30 minutes
5	Pain prevents me from traveling except to receive treatment

Clinical Site Number: Subject Number: **Case Report Form**
Integrity Implants FlareHawk® Study
Follow-up Visit – ODI Score**FOLLOW-UP VISIT**DATE OF VISIT: //
MM DD YYYY**OSWESTRY DISABILITY INDEX (ODI)**Please transcribe answers directly from the patient's medical record.
(Circle score for each section recorded)Not Recorded **Section 1 – Pain Intensity**

0	I have no pain at the moment
1	The pain is very mild at the moment
2	The pain is moderate at the moment
3	The pain is fairly severe at the moment
4	The pain is very severe at the moment
5	The pain is the worst imaginable at the moment

Section 4 – Walking

0	Pain does not prevent me walking any distance
1	Pain prevents me from walking more than 1 mile
2	Pain prevents me from walking more than ½ mile
3	Pain prevents me from walking more than 100 yards
4	I can only walk using a cane or crutches
5	I am in bed most of the time

Section 2 – Personal Care (washing, dressing, etc.)

0	I have no pain at the moment
1	The pain is very mild at the moment
2	The pain is moderate at the moment
3	The pain is fairly severe at the moment
4	The pain is very severe at the moment
5	The pain is the worst imaginable at the moment

Section 5 – Sitting

0	I can sit in any chair as long as I like
1	I can only sit in my favorite chair as long as I like
2	Pain prevents me from sitting more than one hour
3	Pain prevents me from sitting more than 30 minutes
4	Pain prevents me from sitting more than 10 minutes
5	Pain prevents me from sitting at all

Section 3 – Lifting

0	I can lift heavy weights without extra pain
1	I can lift heavy weights but it gives extra pain
2	Pain prevents me from lifting heavy weights off the floor, but I manage if they are conveniently placed e.g. on a table
3	Pain prevents me lifting heavy weights, but I can manage light to medium weights if they are conveniently positioned
4	I can lift very light weights
5	I cannot lift or carry anything at all

Section 6 – Standing

0	I can stand as long as I want without extra pain
1	I can stand as long as I want but it gives me extra pain
2	Pain prevents me from standing more than 1 hour
3	Pain prevents me from standing more than 30 minutes
4	Pain prevents me from standing for more than 10 minutes
5	Pain prevents me from standing at all

Clinical Site Number:

Subject Number:

Case Report Form
Integrity Implants FlareHawk® Study
 Follow-up Visit – ODI Score

OSWESTRY DISABILITY INDEX (ODI) Continued

Please transcribe answers directly from the patient's medical record.
 (Circle score for each section recorded)

Not Recorded

Section 7 – Sleeping	
0	My sleep is never disturbed by pain
1	My sleep is occasionally disturbed by pain
2	Because of pain I have less than 6 hours sleep
3	Because of pain I have less than 4 hours sleep
4	Because of pain I have less than 2 hours sleep
5	Pain prevents me from sleeping at all

Section 8 – Sex Life (if applicable)	
0	My sex life is normal and causes no extra pain
1	My sex life is normal but causes some extra pain
2	My sex life is nearly normal but is very painful
3	My sex life is severely restricted by pain
4	My sex life is nearly absent because of pain
5	Pain prevents any sex life at all

Section 9 – Social Life	
0	My social life is normal and gives me no extra pain
1	My social life is normal but increases the degree of pain
2	Pain has no significant effect on my social life apart from limiting my more energetic interests e.g. sports
3	Pain has restricted my social life and I do not go out as often
4	Pain has restricted my social life to my home
5	I have no social life because of pain

Section 10 – Traveling	
0	I can travel anywhere without pain
1	I can travel anywhere but it gives me extra pain
2	Pain is bad but I manage journeys over two hours
3	Pain restricts me to journeys of less than one hour
4	Pain restricts me to short necessary journeys under 30 minutes
5	Pain prevents me from traveling except to receive treatment

Clinical Site Number:

Subject Number:

Case Report Form
Integrity Implants FlareHawk® Study
Follow-up Visit – VAS Score

Page 1 of 1

FOLLOW-UP VISIT

DATE OF VISIT: / /
MM DD YYYY

VISUAL ANALOG SCALE (VAS)

Please enter the VAS score as documented at the follow-up visit in the medical records for the level of **RIGHT LEG** pain.

VAS **Right Leg** Pain Score: _____ Not Recorded

Please enter the VAS score as documented at the follow-up visit in the medical records for the level of **LEFT LEG** pain.

VAS **Left Leg** Pain Score: _____ Not Recorded

Please enter the VAS score as documented at the follow-up visit in the medical records for the level of **BACK** pain.

VAS **Back Pain** Score: _____ Not Recorded

Clinical Site Number:

Subject Number:

Case Report Form
Integrity Implants FlareHawk® Study
 Intra-Operative Adverse Event Log

INTRA-OPERATIVE ADVERSE EVENT (AE) LOG			No AEs Recorded 			
If Adverse Events have occurred, check “yes” or “no” for each event listed below. If “yes” is marked for an Adverse Event below, please complete all of the columns to the right.						
Adverse Events	Yes / No		Severity	Relatedness	Action Taken	Outcomes
			1- None 2- Mild 3- Moderate 4- Severe 5- Death	1- Device related 2- Procedure related 3- Not related	1- None 2- Medication/Therapy 3- Revision Surgery 4- Additional Surgery 5- Other	1- Resolved 2- Ongoing at 12-month (+/- 3 month) Follow-up 3- Unknown
Device component breakage/fracture	Yes 	No 				
Device malfunction	Yes 	No 				
